Bile acids are the end product of hepatic cholesterol metabolism and act as the main route of excretion for cholesterol. In the adult human two primary bile acids are produced by the liver, i.e. cholic acid and chenodeoxycholic acid. There is some evidence that maternal bile acids gradually rise with advancing gestation, but they usually remain within normal limits (< 14 uMol /L) (Fulton et al., 1983; Pascual et al., 2002). This is in contrast to an ICP pregnancy, where maternal bile acids may be raised to 100 times the upper limit of normal (Walker et al., 2002). In OC, elevated levels of bile acids are also found in the fetal circulation (Laatikainen, 1975).

THE ROLE OF BILE ACIDS IN LIPID AND GLUCOSE METABOLISM:

There is accumulating evidence that FXR, the nuclear hormone receptor responsible for regulation of bile acid homeostasis, also plays a role in the regulation of lipid and glucose metabolism. FXR null mice have been shown to have abnormal blood lipid profiles including elevated plasma cholesterol, low density lipoprotein, high density lipoprotein and triglyceride levels (Ma, 2006). They also exhibit glucose intolerance and reduced insulin sensitivity (Zhang, 2006). Furthermore, ICP patients have raised levels of cholesterol and other lipid parameters (Dann et al. 2006). Specifically, the serum concentrations of low-density lipoprotein (LDL), apolipoprotein B-100, cholesterol and total cholesterol were markedly increased in women with ICP. They have also been shown to have impaired glucose tolerance (Wójcicka-Jagodzińska et al. 1989). Recent data from our group (Martineau et al. 2014, 2015) and others (Marschall et al. 2014) have shown that women with ICP have increased rates of GDM, and implicate raised serum bile acids in susceptibility to diabetes mellitus. Therefore this study will also include women with ICP and superimposed GDM in addition to women with GDM in the absence of ICP. This will enable us to evaluate the impact of cholestasis on the onset of diabetes mellitus in pregnant women.

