GDM is characterized by raised plasma glucose levels in pregnant women (in the absence of pre-pregnancy diabetes mellitus). This condition is associated with large-for-gestational age babies and obstructed labour. Women with GDM have increased risk of subsequent type 2 diabetes mellitus, and if they have this condition in a subsequent pregnancy there is an increased risk of stillbirth. This work is important to understand the causes of the metabolic abnormalities associated with ICP and GDM. If we demonstrate abnormal lipid and glucose profiles, these may be of relevance to the fetal complications of both disorders. It will also be of relevance to the future health of affected women and their children.

2. Hypothesis

There is a relationship between cholestasis and abnormalities of lipid and glucose homeostasis in the mother and baby

That there are abnormalities in bile acid, lipid and glucose homeostasis in women who have previously had ICP compared to controls.

That the placenta may play a role in bile, lipid and glucose homeostasis in ICP cases and controls

Some of the hormonal signals that cause ICP-associated GDM may also cause GDM in non-cholestatic women.

3. Study Objectives and outcomes

Objectives:

- To evaluate the relationship between bile acid, lipid and glucose metabolites in the mother and fetus in ICP, GDM and uncomplicated pregnancies.

Outcomes:

Primary Outcome

- To establish whether raised serum bile acids are associated with abnormalities in cholesterol and triglycerides in the mother and fetus

Secondary Outcome

- To establish the relationship between raised serum bile acids in the mother and fetus and abnormalities in:
 1. Glucose homeostasis
 2. Gut liver signaling hormones related to FGF 19 and C4 levels
 3. Gut hormone secretion

4. Study design

In the non pregnant group we aim to recruit 40 women and 40 matched controls.

In the pregnant women with and without ICP or GDM we aim to recruit 40 in each group together with matched controls.

Written consent will be obtained from all participants.

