Potential participants (both cases and controls) will be identified from the antenatal, obstetric medical and day assessment clinics at Queen Charlotte's and Chelsea Hospital, St Mary's Hospital and other participating units. Midwives and clinicians will be able to refer women who have previously had the conditions after asking them if they would be interested in speaking to someone from the research team regarding the study. Posters will be used in clinical areas and in the cafe area by the antenatal clinic to highlight the research. Women will also be approached directly in these clinics by researchers.

Non-pregnant females may be identified through organisations such as ICP Support and from posters in gynaecology clinics and hospital areas such as the entrance lobby to the main hospital where the shop and cash machine is situated. Clinicians and nurses will

also be able to refer women to the research team after asking the patient if they would be interested in speaking to someone from the research team.

The study will be a case-control study. The pregnancy cohort will be recruited prospectively and will undergo longitudinal study. The non-pregnant participants will also be recruited prospectively but this will be a cross-sectional study.

The study will comprise of the following groups of women. In the groups that comprise pregnant women, maternal blood will be collected at delivery together with placental samples and cord blood (once delivery has taken place and the cord has been clamped and cut). The collection of these types of samples will allow the researchers to fully investigate the metabolites, bile acids and hormones implicated in the disorder together with the potential impact they may have on both mother and baby.

Group 1 are non-pregnant women who have either had normal pregnancies in the past or who have had at least one pregnancy affected by intrahepatic cholestasis of pregnancy (ICP) and/or gestational diabetes mellitus (GDM). This group should only have to attend the study for one day.

Group 2 are women who are identified in early pregnancy. They are either expected to go on to have normal pregnancies or are women with a previous history of ICP and/or GDM. These women may be asked to participate up to three times. This will mean they will need to attend for three separate days. However, this will be linked to their regular visits to the hospital.

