The protocol will be performed only once for women in group 1. It will be performed twice for women in group 2 (at 11-13 weeks and 28-40 weeks). Women in group 2 who go on to develop ICP and/or GDM again in the current pregnancy will be transferred to group 3 at the time of diagnosis. Hence, it is possible that the protocol may be performed four times (11-13 weeks, third trimester, at the time of diagnosis, and 1-4 weeks after starting treatment with ursodeoxycholic acid). In reality this is unlikely to happen and hasn't so far in the study but we would like to retain this option should a participant meet the criteria and be happy to take part four times. For women in group 3 the protocol will be performed twice (at diagnosis and 1-4 weeks after starting treatment with ursodeoxycholic acid). We will record if women are also taking metformin. All of this will be discussed carefully with the participants and all participants will be advised that participating just once will still give us valuable data.

5. Eligibility

Inclusion Criteria

Inclusion criteria:
Cases

- Women with intrahepatic cholestasis of pregnancy, defined as pruritus in pregnancy in association with raised serum bile acids and in the absence of an alternative cause.
- Women with gestational diabetes mellitus (GDM) according to the diagnostic criteria used at the referring centre
- Non-pregnant parous females with previous ICP or GDM.
- Women who are able to give consent.
- Women >16 and <70 years of age.

Controls

- Pregnant women not affected by ICP or GDM .
- Non-pregnant parous females with previous uncomplicated pregnancy.
- Women who are able to give consent.
- Women >16 and <70 years of age.

Exclusion Criteria

Exclusion Criteria:

- Males.
- Non-pregnant females with other medical disorders that can cause liver impairment, abnormal lipid or glucose metabolism in pregnancy, e.g. pre-eclampsia, acute fatty liver of pregnancy, pre-existing diabetes mellitus
- Pregnant females with a history of other medical disorders that can cause liver impairment, abnormal lipid or glucose metabolism in pregnancy, e.g. pre-eclampsia, acute fatty liver of pregnancy, pre-existing diabetes mellitus
- Women who are not able to give consent.
- Women <16 and >70 years of age.

6. Adverse Events

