An **adverse event (AE)** is any untoward medical occurrence in a participant during the study participation days. An existing medical condition (unless it worsens on the study participation days) is not classed as an AE.

All AEs will be recorded in the notes of the participant and on an AE form

A **serious advent event (SAE)** is any untoward and unexpected medical occurrence or effect that:

- Results in death
- Is life threatening to mother and/or baby
- Requires hospitalization
- Results in persistent or significant disorder incapacity ability

All SAEs and action taken as a result will be recorded in the notes of the participant and on an SAE form. An SAE form should be completed and faxed to the Chief Investigator within 24 hours. All SAEs should be reported to the appropriate research ethics committee where in the opinion of the Chief Investigator, the event was:

- 'related' i.e. resulted from the administration of any research procedures; and
- 'unexpected', i.e. an event that is not listed in the protocol as an expected occurrence

Reports of related and unexpected SAEs should be submitted within 15 days of the Chief Investigator becoming aware of the event using the NRES SAE form for non-IMP studies.

Contact details for reporting SAEs

[name] – [name]

[contact] Attention: URGENT - [name]

Please send SAE forms to [name], Dept of Surgery & Cancer, [name]

It is not anticipated that there will be any increased risk of adverse events or serious adverse events in this study. However, it could be that a participant may have an unexpected reaction to the food they eat i.e. an allergic reaction and appropriate action will need to be taken in the event of this happening.

It is also possible that a participant may experience a vasovagal (fainting) episode during venepuncture and appropriate care of the participant will be implemented should this happen.

7. Statistics

- Data analysis will take place at the Institute of Reproductive and Developmental Biology, Imperial College, London. It will be undertaken by the research scientists with statistical advice from the divisional statistician.
- We will use conventional statistical analysis including tests of normal distribution and either Students T-test or the Mann-Whitney U test as appropriate.

8. Procedure for entry to the study, schedule for sample analysis and data recording

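### Late-pregnancy control samples are not tied to the gestation of the case samples: no matching factor is named, and the tests named neither adjust nor pair

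*Protocol*

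**What the plan says.** Section 4 (Study design) places the pregnant controls in group 2, whose members are described as follows: "They are either expected to go on to have normal pregnancies or are women with a previous history of ICP and/or GDM". Their study days are set by gestation: "It will be performed twice for women in group 2 (at 11-13 weeks and 28-40 weeks". The section also says that group 2 women may attend on up to three days, but it gives only these two gestational windows.

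Group 3, the women diagnosed in the current pregnancy, is timed by clinical events: "For women in group 3 the protocol will be performed twice (at diagnosis and 1-4 weeks after starting treatment with ursodeoxycholic acid". No gestational limits apply to the diagnosis sample.

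On matching, section 4 says: "In the pregnant women with and without ICP or GDM we aim to recruit 40 in each group together with matched controls". The summary at the front of the protocol also mentions matched controls. Neither place names a matching factor. Section 7 (Statistics) describes the analysis in one sentence: "We will use conventional statistical analysis including tests of normal distribution and either Students T-test or the Mann-Whitney U test as appropriate".

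The part of section 1 on bile acid homeostasis reports some evidence that "maternal bile acids gradually rise with advancing gestation", and adds that values usually stay in the normal range. The primary outcome in section 3 relates raised bile acids to cholesterol and triglycerides in mother and fetus.

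**The concern.** A control's late sample may be taken at 28 weeks or at 40. A case's sample is taken whenever she is diagnosed. Nothing in the text brings the two distributions of gestation together, and no scheduled group 2 visit falls between 13 and 28 weeks.

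If an analyte changes with gestation and the mean gestation at sampling differs between groups, an unadjusted two-sample test counts the gestational difference as a disease difference. That can create a difference or hide one.

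This is a matter for the protocol and not only for an analysis plan. A covariate can be added later, but samples at gestations where no control was seen cannot.

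**Working it through.** 1. **Inputs from the protocol.** The late control window is 28-40 weeks, the case sample is at diagnosis, and the target is 40 per group (all section 4), read here as 40 cases against 40 controls. The test is the two-sample t-test (section 7). No alpha, power, SD or effect size accompanies the 40, so that target cannot be reproduced. For scale, at two-sided 5% the detectable difference is (1.960 + 0.842) × √(2/40) = 0.63 SD at 80% power, and (1.960 + 1.282) × √(2/40) = 0.72 SD at 90%.

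2. **Assumptions, none of them from the protocol.** Control gestation is uniform over the window, with mean 34 weeks and SD 12/√12 = 3.46. Case gestation is normal with SD 2 and a mean between 28 and 36 weeks. The analyte has residual SD 1 and a linear drift of 0 to 0.10 SD per week. There is no disease effect.

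3. **Bias of the unadjusted difference** = slope × (mean case gestation − mean control gestation). With a case mean of 30 weeks the gap is 30 − 34 = −4 weeks. The bias is then 0.03 × (−4) = −0.12 SD, 0.05 × (−4) = −0.20 SD and 0.10 × (−4) = −0.40 SD.

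4. **Type I error of the t-test** (nominal 5%, 20,000 simulated studies per cell):

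| Case mean, weeks (gap) | 0.03 SD/week | 0.05 SD/week | 0.10 SD/week |
|---|---|---|---|
| 28 (−6) | 12.5% | 25.7% | 72.7% |
| 30 (−4) | 8.3% | 14.0% | 39.8% |
| 32 (−2) | 5.8% | 6.9% | 13.4% |
| 34 (0) | 5.4% | 4.9% | 5.1% |
| 36 (+2) | 5.8% | 7.1% | 13.4% |

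 With zero slope it is 4.7% to 5.2% at every gap.

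5. **Hand check of the 4-week row.** The average within-group variance is 1 + slope² × (12 + 4)/2, where 12 and 4 are the gestation variances of controls and cases. At 0.10 this is 1.08, so the SD is 1.039. The standardised shift is 0.40/1.039 = 0.385, and the non-centrality is 0.385 × √20 = 1.72. The normal approximation gives P(Z > 1.96 − 1.72) ≈ 0.41, against 0.398 simulated. At 0.03 the variance is 1.0072 and the non-centrality is 0.535. The two tails add to about 0.077 + 0.006 = 0.083, as simulated.

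6. **After the change.** Under the same assumptions, regression on gestation at sampling gives a type I error of 4.6% to 5.4%. The plain t-test gives 4.3% to 5.3% when controls are sampled within 1 week of the case's gestation.

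**The case against.** The strongest reply is that controls are described as matched and that 28-40 weeks is only an outer limit. Matching on gestation inside it is entirely possible. This stands: the window is compatible with matching, and if gestation at sampling is the intended factor, most of the problem goes. The protocol does not say that it is.

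A wide window also does not bias by itself; mean gestations must differ. Section 1 says ICP typically presents late in pregnancy, which overlaps the control window, so the gap for ICP may be small. The timing of GDM diagnosis is not given. A reader might infer that the comparison is confounded as it stands, or take the 73% in the table as a forecast. The documents support neither. That cell needs the largest assumed slope and the largest assumed gap together.

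The trend is documented for bile acids only, with qualification, and it is small beside the rise to as much as 100 times the upper limit that section 1 describes in ICP. Drift in cholesterol, triglycerides or glucose is an assumption here.

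Section 7 introduces its tests as included in the analysis, so its list need not be complete, and an analysis plan that is not at hand may add adjustment. That weakens the criticism of the tests but not that of the visit timing. Within group 2, women with and without a previous affected pregnancy share one schedule until any transfer to group 3, so that comparison is aligned.

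A reader might also extend the point to the delivery samples, since "maternal blood will be collected at delivery" along with cord blood and placenta, and section 1 links ICP with spontaneous preterm labour. The 28-40 week window does not govern those samples. The background treats preterm labour as a consequence of the disease, so gestation at delivery may lie on the causal path. Adjusting for it routinely could remove part of the effect or introduce bias.

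**Conclusion.** The point holds for the study-day comparison of pregnant cases with pregnant controls. The protocol fixes case and control sampling times on different bases, names no matching factor, and names only tests that ignore both gestation and matching. Bias is therefore possible, but it is not shown.

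Its size is slope times the gap in mean gestation, and the protocol gives neither. With an assumed drift of 0.03 to 0.10 SD per week, a 4-week gap takes the type I error to about 8% to 40%, and a 2-week gap to about 6% to 13%. It stays near 5% if the mean gestations agree or there is no trend. This is a cheap improvement worth making, not evidence that the study's comparisons are invalid.

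**What to change.** - In section 4, name gestational age at sampling as a matching factor for the pregnant controls.
- Where feasible, book each control's late visit, inside the existing 28-40 week window, close to the gestation of a case's diagnosis sample (for example within 1 week either way).
- Record gestation at every sample.
- In section 7, replace the unadjusted two-sample test for study-day samples with a regression that has gestation at sampling as a covariate, or with a matched analysis.
- Report any cases diagnosed before 28 weeks separately. No scheduled control sample lies between 13 and 28 weeks, so adjustment there would rest on extrapolating the trend.
- Do not adjust cord and delivery samples routinely for gestation at delivery; at most report this as a sensitivity analysis.

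The cost is a small scheduling burden and one extra recorded variable, with no additional participants or visits. Some controls will already be past the target week when a case is diagnosed and cannot be booked to it. The covariate then handles the remaining difference, provided that the trend is modelled adequately and the gestations overlap.

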Group 3 are women who have been diagnosed during their current pregnancy with ICP and/or GDM. These women may be asked to participate twice. This will mean they need to attend for two separate days. However, this will be linked to their regular visits to the hospital which is likely to be at least once a week.

All participants will be given a standard meal (designed by a dietitian) to eat the evening before the study day. Vegetarian and allergy needs will have been taken into account. They will then come to Queen Charlotte's & Chelsea Hospital (or other participating centres) at 8 am the following morning. Each participant will be given a choice regarding the collection of the blood samples. They can have an intravenous cannula inserted or

they can be bled separately each time or have a mixture of both procedures. For example, the first few samples could be taken separately and then a cannula could be inserted for the remaining samples that need to be collected and which are close in timing to each other. The first sample that is collected as soon as they arrive is a fasting sample.

Participants in group 1, 2 and 3 will be involved for most of the day, arriving at 8am in the morning and leaving around 4pm in the afternoon. Following the collection of the fasted sample outlined above participants will be provided with a breakfast. At one and two hours after breakfast blood samples will be taken. Finally, participants will have a standardised lunch with venous blood samples taken 15 minutes before consumption and further blood samples taken at the time of consumption and 20, 60, 120, and 180 minutes post consumption.

In total we will take 9 samples of blood from women in groups 1, 2 and 3. This will constitute a total of no more than 120 mls (approximately 9 tablespoons) of blood being taken on the day of the study.

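### Metformin is the only glucose-lowering drug the protocol says it will record, so in women with GDM the secondary glucose and gut hormone results could not be separated from insulin or other treatment

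*Protocol*

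**What the plan says.** Section 4 (Study design) describes Group 3 in these words: "Group 3 are women who have been diagnosed during their current pregnancy with ICP and/or GDM". Its schedule is "For women in group 3 the protocol will be performed twice (at diagnosis and 1-4 weeks after starting treatment with ursodeoxycholic acid"). Immediately afterwards comes the one sentence on co-treatment, which names metformin only: "We will record if women are also taking metformin".

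Section 1 (Background) explains why diabetes is in scope: "Therefore this study will also include women with ICP and superimposed GDM in addition to women with GDM in the absence of ICP".

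Section 3 sets the primary outcome as "To establish whether raised serum bile acids are associated with abnormalities in cholesterol and triglycerides in the mother and fetus". The secondary outcome begins "To establish the relationship between raised serum bile acids in the mother and fetus and abnormalities in" and lists three items: "glucose homeostasis", gut-liver signalling hormones, and gut hormone secretion.

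Section 7 (Statistics) gives the whole analysis in one sentence: "We will use conventional statistical analysis including tests of normal distribution and either Students T-test or the Mann-Whitney U test as appropriate".

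Two other sources of data appear. Section 8 provides for consented access to medical records, mainly to check earlier data such as a history of ICP or GDM. Section 9.2 describes a medical questionnaire that is completed to check eligibility.

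**The concern.** Glucose-lowering treatment is given because glucose is high, and it acts on glucose, which is one of the measured outcomes. The protocol evidently sees this, since it singles out metformin. It then defines the variable too narrowly: one drug, worded as whether it is taken, with nothing on dose, date of start or change, or timing relative to the nine samples of the study day.

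Two comparisons are exposed.

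- **Between groups.** GDM alone is to be set against ICP with GDM to learn what cholestasis adds. If insulin use differs between these groups, part of any difference in glucose or gut hormones may come from treatment.
- **Between the two Group 3 days.** The first is at diagnosis and the second follows the start of ursodeoxycholic acid by 1 to 4 weeks. In a woman who also has GDM, diabetes treatment may be started or changed in that interval. Her change in glucose then mixes any shift in bile acids with the diabetes treatment.

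Maternal and cord blood are also taken at delivery, so treatment at that time bears on the maternal and fetal glucose results. A later analysis plan can choose covariates, but it cannot adjust for information that nobody collected.

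**Working it through.** The plan gives no figure on this point to reproduce. Section 4 aims for 40 women per pregnant group but states no significance level, power, effect size or standard deviation.

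**Step 1: is the information captured elsewhere?**

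| Source | Stated use | Covers treatment on study days? |
|---|---|---|
| Section 4, co-treatment sentence | Metformin use | Metformin only |
| Section 8, medical records | Mainly previous data, such as history of ICP or GDM | Not stated |
| Section 9.2, questionnaire | Eligibility check before entry | Not stated; contents not given |

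No stated source captures insulin, other drugs, or a change between days.

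**Step 2: how would untracked treatment enter the results?** Let *d* be the shift that treatment causes in a marker, in SD units.

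- Between groups, with treated shares q1 and q2, the bias is (q1 − q2) × *d*. It is zero if the shares are equal.
- Between days, if a share *p* starts or changes treatment, the bias in the mean change is *p* × *d*. If only a share *g* of the women have GDM and a share *r* of those change treatment, then *p* = *g* × *r*. Women with ICP alone dilute the effect.

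**Step 3: illustration.** All inputs are assumed except n = 40: two-sided 5% level, normal approximation, no true effect, SD of the marker (or its change) equal to 1 without treatment.

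- SD with a treated share: s = √(1 + p(1 − p)d²)
- Before-after: T = pd / (s/√n)
- 40 against 40 with an untreated group: T = pd / √(s²/n + 1/n)
- Rejection rate: Φ(T − 1.96) + Φ(−T − 1.96)

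Worked case, p = 0.25 and d = 0.5: bias = 0.125; s = √1.0469 = 1.023; s/√40 = 0.162; T = 0.77; rejection rate = 0.118 + 0.003 = 12.1%.

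| p | d (SD) | Bias (SD) | Before-after, n = 40 | 40 against 40 |
|---|---|---|---|---|
| 0.10 | 0.25 | 0.025 | 5.3% | 5.1% |
| 0.10 | 0.5 | 0.05 | 6.1% | 5.6% |
| 0.10 | 1.0 | 0.10 | 9.3% | 7.2% |
| 0.25 | 0.5 | 0.125 | 12.1% | 8.6% |
| 0.25 | 1.0 | 0.25 | 30.6% | 18.8% |
| 0.50 | 0.5 | 0.25 | 33.5% | 19.6% |
| 0.50 | 1.0 | 0.50 | 80.7% | 55.9% |

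The number of women with both ICP and GDM is not given, so 40 is only a convenient size for the before-after column. With fewer women the rejection rates fall, but the bias in the second step does not.

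**The case against.** The strongest reply is that this argues from silence. Saying that metformin will be recorded does not say that nothing else will be. Dose and timing are usually details of the case report form, and the choice of covariates belongs in an analysis plan. The team also has consented access to medical records, from which treatment might be recovered.

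Part of this stands. The protocol does not fix a yes/no field, and records access means that adjustment is not impossible in principle. But neither the records nor the questionnaire is stated to serve this purpose, and time of last dose on a study day may not be recoverable later. Access shows that the remedy is cheap; it does not show that the data will be gathered.

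A reader might go further and infer that treatment changes will be reported as an effect of ursodeoxycholic acid. The documents do not support that: no objective, outcome or test is defined as an effect of that drug, and section 7 specifies no before-after contrast. A reader might also infer that all 40 women in a group are affected. Women with ICP alone have no stated reason to start glucose-lowering treatment, and nothing says that women with GDM alone receive ursodeoxycholic acid, to which the second Group 3 day is tied. The paired concern therefore centres on women with both conditions.

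**Conclusion.** The point holds as a gap in what is recorded. It is limited to the secondary glucose and gut hormone outcomes in women with GDM. There, an association with bile acids could not be separated from insulin or other glucose-lowering treatment on the data the protocol commits to collect.

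Its size cannot be stated. The illustration runs from negligible to serious depending wholly on two assumed inputs, the share of women affected and the shift per woman, and without the recording the sponsor could not tell which case applies.

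A reader might extend the point to cholesterol and triglycerides. The documents give no basis for that, and no bias in the primary outcome is claimed.

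**What to change.** Replace the metformin sentence in section 4 with one along these lines: *At every study day and at delivery we will record all glucose-lowering treatment (insulin, metformin, other) with dose, start or change date and time of last dose.* Add that the glucose and gut hormone comparisons will also be reported by treatment, or adjusted for it, as a supporting analysis.

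Do not restrict the main comparison to women whose treatment stayed the same. Treatment changes after the first study day in response to glucose, so that restriction would tend to remove women whose glucose worsened and make the remaining change look favourable. Because treatment follows glucose, the adjusted results also need cautious reading, which is why they are supporting.

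The cost is a few extra fields on the study-day and delivery forms. The information can come from the woman on the day and, where needed, from the records she has agreed to have examined. The change concerns data recording and analysis only and alters no one's care.

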Objectives	To establish whether women affected by intrahepatic cholestasis of pregnancy (ICP) and gestational diabetes mellitus (GDM) are predisposed towards developing metabolic disease in pregnancy and in later life. We will do this by measuring metabolic markers and assessing glucose homeostasis.
Population	Pregnant and non pregnant parous women
Eligibility	Pregnant and non pregnant women who have been affected by ICP and GDM together with matched controls

GLOSSARY OF ABBREVIATIONS

OC	Obstetric Cholestasis
ICP	Intrahepatic Cholestasis of Pregnancy
AE	Adverse Event
SAE	Serious Adverse Event
GCP	Good Clinical Practice
CI	Chief Investigator
GDM	Gestational Diabetes Mellitus

1. Background

CLINICAL FEATURES OF INTRAHEPATIC CHOLESTASIS OF PREGNANCY:

Intrahepatic cholestasis of pregnancy (ICP), is a pregnancy-specific liver disorder which typically presents with maternal pruritus (itching) in late pregnancy and affects about 0.7% of women in the UK. Biochemically, it is characterised by liver dysfunction with raised serum bile acids, and clinically by a significantly increased incidence of fetal complications, including spontaneous preterm labour, fetal distress, meconium staining of the amniotic fluid and sudden fetal death (Geenes and Williamson 2009).

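### Does the exclusion for non-pregnant women need a stated reference time (index pregnancy or study entry)?

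*Protocol*

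**What the plan says.** Section 5 of the protocol has two parallel exclusions. For Group 1 it is "Non-pregnant females with other medical disorders that can cause liver impairment, abnormal lipid or glucose metabolism in pregnancy". The next bullet begins "Pregnant females with a history of other medical disorders" and otherwise reads the same. Both give the same examples: "e.g. pre-eclampsia, acute fatty liver of pregnancy, pre-existing diabetes mellitus".

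The age limits are "Women >16 and <70 years of age" for cases and controls alike, and no limit is set on the time since the index pregnancy. Section 4 makes the non-pregnant part cross-sectional and says "The protocol will be performed only once for women in group 1". The synopsis asks whether affected women are "predisposed towards developing metabolic disease in pregnancy and in later life", to be answered by "measuring metabolic markers and assessing glucose homeostasis". Section 4 also says "We will record if women are also taking metformin", among the lines on Group 3.

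**The concern.** The Group 1 exclusion looks carried over from the pregnant groups. It ties the disorder to metabolism in pregnancy, two of its three examples belong to pregnancy, and the third (diabetes) is called pre-existing without saying before what. Yet these women are studied when not pregnant, possibly decades later. Two recruiters could therefore treat a woman who developed type 2 diabetes after her index pregnancy differently.

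The Background (section 1) expects such disease more often in cases: type 2 diabetes after GDM, and biliary disease after ICP. Excluding women with current disease could remove more cases than controls and shrink the difference that Group 1 is meant to show. Admitting them could bring in treated marker values. The two readings also support differently worded conclusions: one about all previously affected women, the other about those without diagnosed disease.

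**Working it through.** **Does the text settle the reference time?**

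- *For the index pregnancy:* the words on pregnancy, two pregnancy-related examples, and section 1, which defines GDM by the absence of diabetes before pregnancy. That last passage defines a case condition; it is not an eligibility rule.
- *For study entry:* the Group 1 bullet uses the present *with*, where the pregnant bullet adds *a history of*. *Can cause* names a class of disorder and does not date its onset. A non-pregnant woman with current type 2 diabetes has a disorder of that class.

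Neither reading is ruled out, but the grammar favours study entry.

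**Does either reading defeat the objective?** The objective concerns predisposition and is pursued through markers; diagnosed disease is not an outcome. Comparing markers in women without overt disease is an ordinary way to study predisposition. Comparing all previously affected women is equally legitimate.

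**Which way would the difference move?** Let x be the excess of cases over controls with later disease, per 40 otherwise eligible women in each group. Let k be the amount, in SD, by which untreated affected women exceed the rest of their group, equal in both groups. Let t be the amount by which treatment lowers their values.

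- Excluding them, against everyone untreated: the difference changes by −x·k/40.
- Admitting them treated, against everyone untreated: it changes by −x·t/40.
- Admitting against excluding: it changes by x·(k − t)/40.

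The protocol gives none of x, k or t. With assumed k = 1, exclusion costs:

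- x = 1: 1 × 1/40 = 0.025 SD
- x = 2: 2 × 1/40 = 0.05 SD
- x = 4: 4 × 1/40 = 0.10 SD
- x = 0: nothing

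For admission against exclusion with x = 4 and k = 1:

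- t = 0.5: 4 × 0.5/40 = +0.05 SD (wider)
- t = 1: 0
- t = 1.5: 4 × (−0.5)/40 = −0.05 SD (narrower)

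Both readings lose signal only against a hypothetical untreated population. Against each other, the sign depends on how complete treatment is.

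**Power.** The protocol states no effect size, alpha or power for 40 v 40. Assuming a two-sided 5% t-test with 80% power, the detectable difference is 0.634 SD (noncentral t). For the extreme assumption x = 4, k = 2, the shift is 4 × 2/40 = 0.20 SD.

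- SD held at 1: 0.634 − 0.20 = 0.434, power 0.483.
- Removing high values also removes variance. Take the remaining women's SD as 1 and no affected controls. The case variance before exclusion is 1 + 0.1 × 0.9 × 2² = 1.36, and the pooled SD is √((1.36 + 1)/2) = 1.086. The difference giving 80% power is then 0.634 × 1.086 = 0.689. After exclusion it is 0.689 − 0.20 = 0.489 with SD 1, power 0.58.

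The answer moves by about 0.10 with the handling of the variance alone, and all of it rests on invented x and k.

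**The case for a change.** The best case for a change is that eligibility belongs in the protocol. An analysis plan cannot restore women who were never recruited, and several units, posters and a patient organisation feed recruitment, so one line would secure a uniform rule at almost no cost. It is true that no sentence gives the reference time, and a sponsor who amends section 5 for other reasons could add it.

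The rest of the case is weaker. The line would only record one of two acceptable populations. Excluding later disease narrows the group; admitting it brings in treated values that an analysis can remove only by losing women. The protocol gives no ground for preferring one.

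Differential exclusion is well supported for previous GDM, but the hypothesis in section 2 about previously affected women concerns ICP. There the Background supports only biliary disease, which matters so far as it counts as a disorder that can impair the liver. The ICP/GDM split of the 40 women is not given.

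The metformin sentence does not show that other drugs go unrecorded. Section 9.2 has a medical questionnaire to check eligibility, whose content is not shown, and section 8 provides for examination of medical records.

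**Conclusion.** No change is needed. The exclusion is loosely worded for Group 1, and an investigator can reasonably apply it as disease present at entry. The other reading would also give a valid comparison, so this is missing detail together with a fair trade-off. The write-up should describe the Group 1 women as they were actually recruited, so that the conclusion matches the population.

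The effect is confined to Group 1. Neither its direction nor its size can be derived from the protocol: the shifts of 0.025 to 0.10 SD assume x between 1 and 4 and k = 1, and the power figures carry too many assumptions to support a claim. This conclusion rests on the reading of the present-tense wording, on markers being the endpoint, and on the same rule being applied to cases and controls.
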